6.0 Enrollment/Randomization

Upon completion of Study Visit 1/Evaluation, the subject will be randomized to initially receive either the PROPRIO FOOT® or the Empower ankle. At study visit 4, the subject will switch to the alternate device.

7.0 Study Procedures

Socket Comfort Score survey: a subjective measure on an 11-point scale of how comfortable the individual feels in the socket. (“On a 0 to 10 scale, if 0 represents the most uncomfortable socket fit you can imagine, and 10 represents the most comfortable socket fit, how would you score the comfort of the socket fit of your artificial limb at the moment?”).

PEQ-13 survey: a 13-question subset of the Prosthesis Evaluation Questionnaire that focuses on the perceived potential for mobility, ambulation, and transfers while using a prosthetic device.

The PEQ-13 uses a 100-point formatted visual analog scale with a scoring range of 0 to 130 in which a higher score indicates high functioning.

CLASS Survey (Comprehensive Lower Limb Amputee Socket Survey): this survey is a self report measure of socket fit that asks the subject to rate stability, comfort, appearance and suspension for their prosthetic socket.

Pressure Sensors (Tekscan F-Socket System): pressure sensors will be placed inside the socket to quantify the amount of force that the participant puts on their residual limb. The sensors will be trimmed to fit the curvature of the socket interface so that reliable measurements can be made in the distal, medial, and proximal regions on the anterior and posterior surfaces of the socket, as well as the fibular head.

Shape Capture: The experimenter will conduct a 3D scan of the residual limb to capture its shape using an optical tracking CAD/CAM system.

K3 Activity Level: Has the ability or potential for ambulation with variable cadence, typical of the community ambulator who has the ability to transverse most environmental barriers and may have vocational, therapeutic, or exercise activity that demands prosthetic utilization beyond simple locomotion.

TEWL: Transepidermal water loss quantifies the functional integrity of the skin. A breach in the physical integrity of the skin (i.e. ulceration) is preceded by breach of functional integrity of the skin, which is indicated by elevated TEWL measurements. This instrument is a non-invasive probe that is placed on the skin that measures water loss coming from the skin. The PI's prior work has shown that, like socket pressure, TEWL is affected by the type of suspension.

Weight: We will obtain weight at all study visits

Laser Speckle Imaging (LSI): A non-invasive device that measures blood flow, referring to the rate of blood flow through the vessels serving the skin.

Timed Up and Go test: The subject will stand from a seated position and walk approximately 3 meters and then return to a seated position. This activity will be timed by research staff.

Motion Capture and Gait Analysis: Reflective markers will be placed on the subject with the goal of recording the movement of the subject during ambulation. Upon completion of the activities, motion analysis will be interpreted and will provide a clear and detailed picture of how a participant moves in space. Gait and Motion Analysis is of particular interest to understand how a participant's gait can affect the amount of pressure that they place on their residual and intact limbs.

8.0 Study Calendar

	Week 0	Study Visit 1: Evaluation (CWC) Week 1	Study Visit 2: Baseline (Goodman Hall) Week 2 (+ 7 days)	Study Visit 3 (CWC) Week 6 (+/- 7 days)	Study Visit 4 (Goodman Hall) Week 7 (+/- 7 days)	Study Visit 5 (CWC) Week 11 (+/- 7 days)	Study Visit 6 (Goodman Hall) Week 12 (+/- 7 days)
Device randomized		X					
Informed consent ¹	X	X					
Enrollment		X					
Socket Comfort Score		X		X		X	
CLASS Survey		X		X		X	
PEQ-13		X		X		X	
Weight recorded		X	X	X	X	X	X
TEWL measurement		X		X		X	
Laser Speckle Imaging (LSI)		X		X		X	
Pre-fitting and adjustments		X		X		X	
Digital shape capture			X		X		X
Administer pressure sensors			X		X		X
Ambulation trials (level-ground, stairs, and ramps)			X		X		X
3D motion capture			X		X		X
Timed Up and Go			X		X		X
Fitting of research device			X		X		
Adverse event review			X	X	X	X	X

Footnote: ¹consent could be at either week 0 or study visit 1, at the convenience of the subject

9.0 Reportable Events

Protocol deviations and Unanticipated Problems involving risks to subjects or others, Adverse Events, and Other Problems will be reported to Indiana University per IU IRB reporting requirements.

Unanticipated problems can occur in any type of research (medical or non-medical) and may include occurrences such as adverse events, subject complaints, protocol deviations, and other untoward events involving risk. Events requiring prompt reporting by investigators and research staff may involve physical, psychological, social, legal, or economic harms.

Event reports and accompanying information will be screened for completeness by research staff members, additional clarifications will be requested from the investigator, as necessary. Research staff members and the principal investigator will make an initial determination about whether the event represents a possible unanticipated problem involving risks to subjects or others and/or potential noncompliance. Reports of events determined during screening to represent possible unanticipated problems involving risks to subjects or others and/or serious/continuing noncompliance will be forwarded to the IRB for convened review. Reports of events that do not meet the requirements for prompt reporting may be reported at time of study renewal.

10.0 Payment to Participants

Participants will be compensated for their time and effort as follows with a study payment card that can be used like a debit or credit card, all payments will generally be available within 24 hours of the study visit.

- Study Visit 1: \$50
- Study Visit 2: \$50
- Study Visit 3: \$100 (Payment of \$150 will be compensated if opted for 4 study visits)
- Study Visit 4: \$50
- Study Visit 5: \$50 (Payment of \$150 will be compensated if opted for 4 study visits)
- Study Visit 6: \$100

Since the visits are going to be long, lunches will be provided. Lunches will be catered, and no reimbursements or vouchers will need to be administered. The participant will not be charged for their lunch.

11.0 Safety Monitoring Plan

A physician who is a member of the study team and the study coordinator will meet at the following timepoints to review the study data and any adverse events to ensure continued subject safety: prior to initiation of the study, after the 5th subject is enrolled, after the 10th subject is enrolled, and 60 days following the conclusion of study procedures for all subjects.

12.0 Study Withdrawal/Discontinuation

Patients will be informed during the informed consent process (in writing and verbally) that they are free to withdraw from the trial at any time. The investigator may exercise his medical judgement to terminate a patient's participation in the trial due to clinically relevant changes in any clinical or laboratory parameter. The Sponsor-Investigator also reserves the right to discontinue/terminate the trial at any time.

Discontinuation criteria for individual subjects include: (1) Non-compliance with the inclusion/exclusion criteria, (2) treatment non-compliance, such as use of another ankle

prosthesis, (3) withdrawal from the study due to reasons not related to the treatment, (4) prosthetic socket becomes uncomfortable.

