The most common quantitative measure of prosthetic fit is pressure inside the socket during locomotion activities, and a wide range of measurement techniques have been pursued [41, 42]. Results show that mediolateral pressures tend to be less than anterior and posterior pressures, with anterior pressures typically being the highest [43]. Walking on slopes and stairs is of particular interest since internal stresses are known to be elevated in these cases [44] and pressure in level-ground walking is a poor predictor of that in these more challenging circumstances [45]. In stair ascent, the highest pressures are located in the proximal region of the anterior surface [46, 47], whereas they shift to the distal region with stair descent [47]. Gait and Motion Analysis is of particular interest to understand how a participant's gait can affect the amount of pressure that they place on their residual and intact limb. Beyond these activity-specific results, socket pressure has also been shown to be influenced by the type of suspension [43, 46], the type of foot [48, 49], and the alignment of the prosthesis [50–54].

Measuring fit via socket pressure, though, remains one step removed from limb health, the actual quantity of interest. More direct measures of limb health include transepidermal water loss (TEWL) for quantifying the functional integrity of the skin and laser speckle imaging (LSI) for quantifying skin perfusion. The PI's prior work has shown that, like socket pressure, TEWL is affected by the type of suspension (Fig. 3), but perfusion is not necessarily (Fig. 4) [62]. No studies to date have examined the effects of active lower-limb prostheses, neither micro-controlled nor powered, on these direct measures of limb health.

Active prostheses like the PROPRIO FOOT® and Empower ankle offer great potential to more completely restore the locomotor capabilities of individuals with transtibial amputation, perhaps enhancing RTD for military personnel. As with all prosthetic components, though, these active devices are of little use if they induce pain and/or injury at the residual limb to the degree that the user will simply not wear them. Overall, this project seeks to understand and quantify the effects of powered transtibial prostheses on socket loading and direct measures of residual limb health so as to inform the optimization of prosthesis fit.

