3.0 Outcome Measures/Endpoints

3.1 Primary Outcome Measures

Determine the effects of a powered transtibial prosthesis on the socket pressure for level-ground walking, stair ascent/descent, and ramp ascent/descent in comparison to a microprocessor-controlled prosthesis and a passive prosthesis at 4 weeks.

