3.2 Secondary Outcome Measures

Determine the relative impact on residual limb health of the use of a powered prosthesis, a microprocessor-controlled prosthesis, and a passive prosthesis for individuals with transtibial amputation at 4 weeks.

- Transepidermal water loss (TEWL) measurements at 4 weeks
- Skin perfusion measurements and analysis at 4 weeks
- PEQ, CLASS and Comfort Score responses at 4 weeks

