- Body weight recorded.
- Multiple ambulation trials will be performed including level-ground walking tasks, stair ascent/descent tasks, and ramp ascent/descent trials
- 3D motion capture using the motion capture system will be conducted with the use of an electronic device that measures and reports a body's specific force, angular rate, and sometimes the orientation of the body, which are placed on subjects clothing to capture movement
Walking tasks and ascending/descending tasks on stairs and ramps will be completed with the use of force-sensing pads
- Timed get up and go test will be performed: subject will stand from seated position and walk 3 meters and then return and sit down
- Prosthetist will fit the participant with the research foot that was randomized to them
 - 15-30 minutes of usage of the prosthetic foot will be provided for acclimation
- Subject will repeat the level-ground, stair, and ramp trials with the new prosthetic foot (Foot A)
- Prosthetist will remove pressure sensors from the socket after ambulation and recording will be terminated

Upon completion of baseline, the subject will wear the research device (Foot A) for 4 weeks to become accustomed to the new technology through its exclusive use in place of their standard-of-care prosthetic foot.

Study Visit 3: After the four-week acclimation period, the subject will return for Visit 3 at IUH Methodist Hospital. A window of +/- 7 days will be implemented, ensuring the duration to complete Visit 3 remains consistent among all participants. The following activities will take place during Visit 3:

- Participant's weight will be captured
- Research personnel will administer surveys (Socket Comfort Score, CLASS and PEQ-13)
- Non-invasive limb health measurements performed (TEWL and Laser Speckle Imaging (LSI))

- Licensed prosthetist will perform pre-fitting and adjustments on the patient, ensuring the other research foot (Foot B) will be ready to deliver during participant's next visit

Study Visit 4 (Study Visit 3 if opted for 4 Study Visits): Study Visit 4 will occur within a week after Visit 3 with a window of 0-7 days. This visit will take place at Noyes. The following activities will take place:

- Digital shape capture will be performed
- Administer pressure sensors on participant's research socket and recording will be initiated using Foot A
- Body weight recorded.

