13.0 Statistical Considerations

This longitudinal study will compare the effects of the three prostheses on the various measured quantities for each subject. Motion capture data will be filtered with an 8 Hz Butterworth low-pass filter, and ground reaction forces will be filtered with a 50 Hz critically damped filter. These data will be collected and analyzed primarily to interpret how differences in kinematics and kinetics associated with the prostheses contribute to corresponding differences in socket pressure and limb health measures. All pressure measurements will be normalized with respect to body weight as measured during the session of data collection. Mean peak pressure within and pressure-time integrals across each gait cycle will be calculated for each sensor location. The peak pressure provides an indication of the maximum loading at any location, while the pressure-time integral combines both the magnitude and duration of loading since both are relevant for limb health.

The 3D scans of the residual limb will be compared between Visits 2 and 4 and between Visits 4 and 6 as a means of interpreting whether significant changes in socket pressure are due to corresponding changes in residual limb volume and/or shape. Both TEWL and skin perfusion, i.e., laser speckle imaging, will be measured or quantified into continuous scales from a three-period, baseline, 30 min post-fitting and 4 weeks post-fitting. The values will be normalized using the values collected from the corresponding reference site [62].

Mean peak socket pressure will serve as the primary outcome measure, with particular emphasis on the proximal region of the anterior surface. Pressure-time integrals will serve as the secondary outcome measure, again emphasizing the same region. TEWL values will be used as the primary outcome measure of overall limb health, while skin perfusion will be the secondary outcome measure. For each measure, comparisons among the three prostheses will be made via a repeated measures ANOVA with Bonferroni correction. For both aims, the survey responses will provide a means of evaluating whether subject impressions aligned with quantitative measures of socket pressure and limb health.

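### The plan has no rule for subjects stopped for an uncomfortable socket or for using another prosthesis: a classical repeated measures ANOVA would discard their usable records, and stops by device go unreported

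*Combined protocol and SAP*

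**What the plan says.** Section 12.0 gives four reasons for discontinuing an individual subject. Two matter here: "2) treatment non-compliance, such as use of another ankle" prosthesis, and "4) prosthetic socket becomes uncomfortable".

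The outcomes are tied to four weeks of wear. Section 3.1 sets the powered foot "in comparison to a microprocessor-controlled prosthesis and a passive prosthesis at 4 weeks"; Section 3.2 lists "Transepidermal water loss (TEWL) measurements at 4 weeks", together with perfusion and survey responses.

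For the analysis, Section 13.0 says that, for each measure, "comparisons among the three prostheses will be made via a repeated measures ANOVA with Bonferroni correction". It names no analysis set, rule for incomplete subjects or sensitivity analysis.

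Three other places touch on stops or missing data. The calendar (Section 8.0) has adverse event review from Visit 2, Section 11.0 sets safety meetings, and Section 14.2 monitors follow-up and missing data. None says how a stopped subject enters the device comparison, and none reports stops by device.

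**The concern.** A subject whose socket becomes uncomfortable, or who goes back to another foot, may well be one whose pressure or skin measures would have been unfavourable. If such subjects leave the comparison, three things follow.

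- **Data already collected are wasted.** The feet are worn in sequence, so a stop on the first foot (Foot A) removes the 4-week value of both feet. A stop on the second (Foot B) removes only its own 4-week value, yet a complete-case analysis drops the whole subject.
- **The comparison may be tilted.** If outcome-related stops fall on one foot, that foot looks better than it is. The Empower-PROPRIO difference is then understated if that foot is the worse one and overstated if it is the better one. If one discomfort threshold applies to both feet, the research-foot versus passive contrast is tilted towards the research foot.
- **Stopping itself goes unseen.** Section 1.0 says active devices are of little use if they cause pain or injury "to the degree that the user will simply not wear them". Stops by device bear on that, but are not among the outcomes. The comfort surveys at Visits 3 and 5 describe only subjects who reach those visits.

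**Working it through.** The plan states no sample size, standard deviation, effect size or dropout rate, so there is no figure to reproduce. Section 11.0, with a review after the 10th subject, implies at least 10 subjects. Everything from step 2 on is illustration.

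**1. Records left after a stop (Sections 5.0 and 8.0, pressure)**

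| Stop during | Passive | Foot A, 4 weeks | Foot B, 4 weeks | Immediate records |
|---|---|---|---|---|
| Foot A | yes | no | no | Foot A (Visit 2) |
| Foot B | yes | yes | no | Foot A (Visit 2), Foot B (Visit 4) |

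Complete-case ANOVA uses neither subject. The immediate records are scheduled, but Section 13.0 does not say that they enter the pressure comparison. TEWL and perfusion are scheduled at Visits 1, 3 and 5 only, so their pattern is the same without the immediate records. Section 13.0 does describe "baseline, 30 min post-fitting and 4 weeks post-fitting" for these two measures. The calendar has no such 30-minute reading, and the two sections need reconciling.

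**2. Bias when stops fall on one foot**

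Assumptions: each record has SD 1; the between-subject share of variance is v = 0.4 or 0.6; pressure correlates with discomfort at r = 0.3 or 0.6. A subject stops when discomfort plus independent standard normal noise passes a threshold, with probability p. The complete-case shift in Empower-PROPRIO, in favour of that foot, is

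bias = r(1 - v) φ(z) / [(1 - p)√2], with z the upper-p normal quantile.

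The factor r(1 - v) runs from 0.3 × 0.4 = 0.12 to 0.6 × 0.6 = 0.36.

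| p | φ(z) | φ(z)/[(1 - p)√2] | Bias (SD) |
|---|---|---|---|
| 0.1 | 0.1755 | 0.138 | 0.017 to 0.050 |
| 0.2 | 0.2800 | 0.247 | 0.030 to 0.089 |
| 0.3 | 0.3477 | 0.351 | 0.042 to 0.126 |

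**3. Bias when both feet share one threshold**

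This was simulated with 400,000 subjects and a true Empower excess of 0.5 SD. At 10/20/30% average loss per foot, complete-case bias is 0.01-0.03 / 0.01-0.04 / 0.02-0.05 SD for Empower-PROPRIO. For Empower-passive it is 0.02-0.06 / 0.03-0.10 / 0.04-0.14 SD, in favour of Empower. The share of subjects lost is 18% / 34-35% / 48-49%.

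**4. Sampling error and lost precision**

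At an assumed N of 15 with random loss, complete subjects number 15(1 - p)² = 12.2, 9.6 and 7.4. The standard error of a paired difference is √[2(1 - v)/n]. It runs from √(0.8/12.15) = 0.26 to √(1.2/7.35) = 0.40, or up to 0.42 when averaged over the random number of complete subjects. The biases in steps 2 and 3 lie below this.

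A model on all available pressure records (passive, and each foot immediate and at 4 weeks; subject-by-device variance 0.2) lowers the standard error as follows:

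| Contrast | 10% loss | 20% loss | 30% loss |
|---|---|---|---|
| Empower-PROPRIO | about 3% | 6-7% | 9-11% |
| Empower-passive | about 6% | 12-13% | 17-19% |

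A separate calculation with the period term put the ranges at about 2-10% and 5-17%. With variances estimated by REML, the gains were 0-13% and 4-21%. For TEWL with three records they were only 0-3% and 3-10%.

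**5. An extreme case**

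If stopping were decided by Empower pressure alone (v = 0.5), the bias would be (1 - v)φ(z)/(1 - p). At 30% that is 0.5 × 0.3477/0.7 = 0.25 SD. With N = 15, 10.5 subjects would then be complete and the standard error √(1/10.5) = 0.31 SD, still larger than the bias.

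**The case against.** **The plan does not say that incomplete subjects are dropped.** This stands. Listwise deletion belongs to the classical form; a subject-plus-device ANOVA fitted by least squares keeps partial data, and Section 13.0 does not exclude it. A reader might infer that subjects will be lost, but the documents support only that their handling is unspecified and that the usual form of the named method would lose them.

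**The bias rests wholly on assumptions.** This also stands. Nothing in the documents suggests that 30% would stop on each foot, which means about half of all subjects leaving.

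**A mixed model hardly touches informative stopping.** Largely true. With Empower-only loss at 30%, bias falls only from 0.04-0.13 to 0.03-0.11 SD. With three records and a shared threshold, the Empower-passive bias is 0.05-0.14 SD in complete cases and 0.05-0.15 SD in the model. The model earns its place by keeping data; the shift analysis addresses the informative part.

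**An uncomfortable socket is not a verdict on the foot.** Correct. The criterion concerns the socket, and counts of stops do not measure how much a foot was worn. In a small trial the table will have sparse cells, so it should be descriptive.

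**Stops would be noticed anyway.** Probably, through adverse event review and data monitoring. But noticing a stop is not a rule for analysing it, and no section commits to reporting stops by device.

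**Conclusion.** The gap is real and modest. Two stopping reasons may be related to the outcomes, the one named analysis would in its classical form discard usable pairs, and stops by device are not reported.

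The true size cannot be found from the documents. Under the assumptions shown, bias is at most about 0.14 SD, below sampling error at N = 15. The surer cost is precision: a standard error higher than need be, by an amount that all available records would cut by roughly 2-11% (Empower-PROPRIO) and 5-19% (foot-passive). For Empower-PROPRIO the gain may be near nil at low loss or for TEWL.

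A reader might go further and infer that one foot will look materially better because its worst-affected users have gone. The documents do not support that: they give no attrition figure, do not attribute discomfort to either foot, and do not fix the form of the ANOVA. This is a cheap improvement, not a flaw that invalidates the comparison.

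**What to change.** Leave the stopping criteria as they are.

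1. **Section 13.0, analysis.** State that the 4-week device contrasts are estimated from all available records.
   - *Pressure:* a linear mixed model with device-by-time means (passive; each research foot immediate and at 4 weeks), a period term for the research feet, a subject effect and a random subject-by-device effect. Use Kenward-Roger or Satterthwaite degrees of freedom and keep the Bonferroni correction. Whether subject is fixed or random is for the trial statistician. Battery-off trials are a separate condition and stay out. Section 5.0 gives no battery setting for the first Foot A trials at Visit 2, so confirm it before using them.
   - *TEWL and perfusion:* with three scheduled records, a subject + device + period model fitted to all available records is enough. If the 30-minute reading is in fact taken, the pressure form applies.
2. **Reporting.** Tabulate discontinuations by device worn, period and reason, descriptively.
3. **Sensitivity analysis.** For subjects who stopped for discomfort or for using another prosthesis, impute from the model the missing 4-week value of the foot worn at the stop. Shift it unfavourably by 0 to 1 SD of that outcome, and report where the conclusion changes.

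The cost is a rewritten paragraph, one table and a little more analysis work, with no added visits or measurements. The model in item 1 does not remove bias from loss that depends on unobserved values; item 3 shows how much such loss would matter. For TEWL, items 2 and 3 carry most of the benefit.
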